9.4 DATA SOURCES

The study will use data from the federal Medicare program on elderly beneficiaries consistently enrolled in traditional, or fee-for-service, Medicare insurance coverage for hospital (Part A), physician (Part B) and pharmacy (Part D) claims. As of October 2021, there were over 36 million beneficiaries in traditional Medicare. The study will focus on enrollment and claims data from October 1, 2013, through December 31, 2020. Access to these data has been obtained by [REDACTED] through the [REDACTED].

This data source was selected for multiple reasons. First, Medicare data capture the preponderance of IPF cases. In a study reported by Ipatova et al. (2019), 76% of patients on nintedanib or pirfenidone were ≥ 65 years of age. Second, Medicare claims are comprehensive in their inclusion of covered services, including outpatient prescription drugs (through Medicare Part D). Third, there is comparatively little turnover among Medicare beneficiaries compared with commercial insurance enrollees, which means that it is possible to follow Medicare beneficiaries for longer periods on average and more patients will qualify for a study requiring a given minimum continuous coverage period. Fourth, Medicare claims were used in the prior study of nintedanib adherence, so it is natural to continue using them for this study.

9.5 STUDY SIZE

In the prior study, there were 18,733 Medicare beneficiaries with at least one claim for nintedanib between 10/01/2014 and 12/31/2018. After sample selection criteria were applied, the final analytic sample consisted of 1,798 patients (**Figure 3**).

[figure not shown]

Figure 3. Sample selection in the prior study of nintedanib adherence trajectories

9.6 DATA MANAGEMENT

Data manipulation and analysis will be conducted by [REDACTED]. Pursuant to requirements guiding participation in the [REDACTED] Innovator program, [REDACTED] staff will access the Medicare claims and enrollment data only through the [REDACTED]. As such, [REDACTED] will not directly possess any beneficiary-level [REDACTED] data, and the only data to be downloaded from the [REDACTED] will be summary-level statistics.

Data security will be assured along two dimensions. First, the data will reside only in [REDACTED] secure [REDACTED] environment. [REDACTED] staff have completed a rigorous identity verification process to gain access to the [REDACTED]. [REDACTED] prohibits any patient-level data from

Proprietary confidential information © 2023 Boehringer Ingelheim International GmbH or one or more of its affiliated companies being copied from the [REDACTED]; only aggregated data based on at least 11 patients is allowable. Second, only a limited set of patient identifiers will be present in the data, including residential ZIP Code and full dates of health insurance enrollment and claims and subject's birth and death dates. The unique patient ID used by [REDACTED] is a synthetic identifier, and no [REDACTED] study staff will have access to the linking file to real subject identifiers.

Additionally, study documents, including synopsis, protocol, and final results as well as publications, will be archived on the [REDACTED] Team site.

9.7 DATA ANALYSIS

9.7.1 Main analysis

Descriptive statistics of the covariates will be calculated stratified by the five categories of patients' adherence trajectory group membership, after assigning patients to the group for which they had the highest posterior probability of membership as estimated in the GBTM (from the prior study). Tests of joint equality across groups will be computed using ANOVA and nonparametric Kruskal-Wallis rank tests for continuous measures and χ^2 tests for categorical measures.

Mean outcomes will be compared between pairs of nintedanib adherence trajectory membership categories (referent group: highly adherent) using a regression modeling framework. Unadjusted means will be compared first using an "empty" linear regression model specification (with no covariates or weights) that makes standard errors robust to heteroskedasticity of unknown form. Adjusted means will then be compared using a "doubly robust" generalized linear model (GLM) specification that also uses heteroskedasticity-robust standard errors. More detail about the double-robustness is provided below.

The functional form of the GLM will be selected for each outcome based on its observed distribution in the data. The binary outcome of "any hospitalization" will likely be modeled with logistic regression. The non-negative "total LOS" outcome may be modeled with a quasi-maximum likelihood Poisson model if the proportion of patients with zero days of hospitalization is sufficiently low (less than 10%), or a two-part model (e.g., logistic model of any hospitalization vs. none and a simultaneously estimated Poisson model of total LOS conditional on having positive LOS) if not (Belotti et al., 2015). Similarly, if the "total medical costs" outcome has a pile-up at zero, a two-part model will be estimated; if not, a GLM with a log link and a distribution family decided by application of the modified Park test will be estimated (Manning, 1998).

Potential confounding by observed covariates will be addressed in two ways, thus leading to "doubly robust" estimates. The first way is to calculate two sets of observation-level weights that balance covariates across exposure categories: inverse probability of treatment weights (IPTWs) and weights derived from a marginal mean weighting through stratification (MMWS) procedure (Hong, 2012; Linden, 2014). To generate the weights, a multinomial logit model of nintedanib adherence trajectory group category will be estimated as a function of the covariate roster. Predicted probabilities (i.e., propensity scores) for each category will be generated from the model results and used to calculate both the IPTW and MMWS

Proprietary confidential information © 2023 Boehringer Ingelheim International GmbH or one or more of its affiliated companies weights. Because multiple exposure categories are to be compared, the weights will provide estimates of the average treatment effect (ATE) (and not the average treatment effect on the treated [ATT]).

The second way confounding will be addressed is through regression adjustment; that is, observed covariates will be added to the GLM specification. Combining weighting with regression adjustment yields a double robustness property that attenuates bias in the case when either the treatment model (i.e., the multinomial logit model of exposure category) or the outcome model (i.e., the GLM of the health care resource use or spending outcome) is misspecified (Linden et al., 2016).

To facilitate interpretability, the regression model results will be transformed back to the scale of the outcome variable. Average marginal effects and their 95% confidence intervals (CIs) will be calculated using the delta method. Data preparation will be performed using SAS 9.4 (██████████) and data analysis will be conducted using Stata 17 (██████████).

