9.3.3 Covariates

Study covariates are listed here and will be measured at the index date or during the 12 months prior.

Variable	Description
Demographic and socioeconomic characteristics	
Age	Age as of index date in years rounded to the nearest whole number will be calculated based on the difference between the beneficiary's birth date and index date.
Age group	Age group will be a categorical variable for age defined as one of 65–74, 75–84, 85+.
Female	Female will be a binary indicator for whether the beneficiary was female as indicated on the enrollment record covering the index date.
Race	Race will be a categorical variable for the beneficiary's self-reported race/ethnicity taking the

BOEHRINGER INGELHEIM Group of Companies

NIS Protocol

BI Study Number 1199-0520

Page 18 of 35

c42255024-02

Proprietary confidential information © 2023 Boehringer Ingelheim International GmbH or one or more of its affiliated companies

Variable	Description
	categories Non-Hispanic White, Black or African-American, Other, Asian/Pacific Islander, Hispanic, American Indian/Alaska Native, and unknown race from the enrollment record covering the index date.
Census region	Census region will be a categorical variable defined by categorizing the beneficiary's state of residence into Census regions (Northeast, South, Midwest, West) from the enrollment record covering the index date.
Index year	Index year will be a categorical variable defined as the year of the index date and will take the values, 2014, 2015, 2016, 2017 or 2018.
Social deprivation index	Social deprivation index will be a continuous variable ranging between 0 and 100 representing the Social Deprivation Index for the beneficiary's residential ZIP Code as calculated by the Robert Graham Center. Social Deprivation Index "is a composite measure of seven demographic characteristics collected in the American Community Survey (ACS): percent living in poverty, percent with less than 12 years of education, percent single parent household, percent living in rented housing unit, percent living in overcrowded housing unit, percent of households without a car, and percent non-employed adults under 65 years of age." This version was calculated in 2015 using data from 2015 and updates the original version created by Butler et al. (2013). Higher values for the Social Deprivation Index indicate more social deprivation.
Clinical characteristics	

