Sleep apnea	A binary indicator for whether the beneficiary had a diagnosis code for obstructive sleep apnea on at least one inpatient, outpatient or Carrier claim that occurred during the baseline period.
Lung biopsy	A binary indicator for whether the beneficiary had a diagnosis or procedure code for a lung biopsy on at

BOEHRINGER INGELHEIM Group of Companies

NIS Protocol

BI Study Number 1199-0520

Page 20 of 35

c42255024-02

Proprietary confidential information © 2023 Boehringer Ingelheim International GmbH or one or more of its affiliated companies

Variable	Description
	least one inpatient, outpatient or Carrier claim that occurred during the baseline period.
HRCT scan	A binary indicator for whether the beneficiary had a procedure code for a high-resolution computerized tomography scan on at least one inpatient, outpatient or Carrier claim that occurred during the baseline period.
Oxygen	A binary indicator for whether the beneficiary had a diagnosis, procedure revenue center code for oxygen therapy or supplemental oxygen on at least one inpatient, outpatient, Carrier, skilled nursing facility, home health or durable medical equipment claim that occurred during the baseline period.
Pulmonary rehabilitation	A binary indicator for whether the beneficiary had a procedure or revenue center code for pulmonary rehabilitation services on at least one inpatient, outpatient, Carrier, skilled nursing facility, home health or durable medical equipment claim that occurred during the baseline period.
Ventilator use	A binary indicator for whether the beneficiary had a diagnosis or procedure code for ventilator use on at least one inpatient, outpatient or Carrier claim that occurred during the baseline period.
COPD	A binary indicator for whether the beneficiary had a diagnosis code for chronic obstructive pulmonary disease on at least one inpatient, outpatient or Carrier claim that occurred during the baseline period.
Hypoxia	A binary indicator for whether the beneficiary had a diagnosis code for hypoxia on at least one inpatient, outpatient or Carrier claim that occurred during the baseline period.
Pharmacy use and spending	
Medication count	The count of the number of unique outpatient prescription medications for which beneficiary has Part D claims during the baseline period

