9.9 LIMITATIONS OF THE RESEARCH METHODS

The study has several limitations, including:

- The data source consists of administrative claims data, which do not include important determinants of health care resource use and cost outcomes that may be correlated with the adherence exposure, such as IPF disease severity.
- Although the outcomes should be measured accurately, the adherence exposure is necessarily based on prescription fill data from claims and may mismeasure actual nintedanib use.
- Sample selection bias may arise from the design decision to exclude patients who do not have at least 12 months of follow-up data after nintedanib initiation for primary outcomes (and 24 months for secondary outcomes).
- Generalizability may be limited to IPF patients who are continuously covered under fee-for-service Medicare, including Parts A, B and D.

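### The covariate roster has no direct measure of general adherence behaviour, so the trajectory-group contrasts may carry residual healthy-adherer bias of unknown size and direction

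*Combined protocol and SAP*

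**What the plan says.** Section 9.7.1 says "Potential confounding by observed covariates will be addressed in two ways": weighting and regression. For the weights, "a multinomial logit model of nintedanib adherence trajectory group category will be estimated as a function of the covariate roster"; for the regression, "observed covariates will be added to the GLM specification". It describes the weighted estimate as an average treatment effect.

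Section 9.3.3 supplies the list: "Study covariates are listed here and will be measured at the index date or during the 12 months prior". The entries are demographics, region, index year, social deprivation index, a comorbidity index, respiratory diagnoses and procedures, medication count, pharmacy spending, medical use and spending by setting, ED visits, pulmonology visits, and whether the index prescriber was a pulmonologist. The nearest entry to medication behaviour is medication count: "The count of the number of unique outpatient prescription medications for which beneficiary has Part D claims during the baseline period".

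Section 9.9 warns that claims omit important determinants of the outcomes that may be correlated with adherence, and gives one example: "such as IPF disease severity". No sensitivity analysis for unmeasured confounding is planned.

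**The concern.** Trajectory group is assigned from how regularly a patient refilled nintedanib over 12 months. Patients who refill one drug reliably may also take other medicines reliably, use preventive care, and differ in self-care or access. That general trait is a plausible common cause of trajectory group and of later cost and hospitalization. If it is not adequately controlled, part of the contrast with the highly adherent group belongs to the kind of patient and not to nintedanib adherence.

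This matters because of how the results are to be used. The objectives speak of association, but 9.7.1 uses average-treatment-effect language, and Section 7 expects the findings to help clinicians and payers improve nintedanib adherence. That use needs a contrast that reflects nintedanib adherence itself.

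**Working it through.** **1. Does any roster item measure the trait?** Reading 9.3.3 entry by entry:

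- Medication count records how many different drugs were filled, not how regularly. Section 7 reports that, in the prior study, taking an additional baseline medication was associated with higher odds of being in at least one lower-adherence group. Count is therefore not a simple marker of good adherence here.
- Pulmonology visits, HRCT and pulmonary rehabilitation record contact with care. They mix severity, access and engagement.
- Spending and use variables record the amount of care.
- There is no PDC or persistence measure for other medicines and no vaccination, screening or preventive-visit indicator.

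**2. Can the planned method make up for it?** Double robustness protects when either the treatment model or the outcome model is misspecified. Both draw on the same roster. A confounder missing from both is controlled only as far as the listed covariates act as proxies for it.

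**3. Are data available?** Yes. Section 9.2.1 says Part D claims carry fill date and days' supply. Section 9.2.2 requires at least 12 months of Parts A, B and D before the index date. Section 7 shows the team has already computed PDC from these fields for nintedanib.

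**4. How large could the bias be?** The plan gives no figure to reproduce: no effect size, cost SD or power calculation. Both illustrations below use assumed inputs, treat the trait as unrelated to every roster item (so they are before adjustment), and set the true nintedanib effect to zero.

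*Cost ratio.* Let a fraction p1 of highly adherent patients and p0 of a declining group have the trait, and let the trait lower cost by a proportion d. The apparent ratio, declining to highly adherent, is (1 − p0·d)/(1 − p1·d). With p0 = 0.5:

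| p1 | d = 0.10 | d = 0.15 | d = 0.20 |
|---|---|---|---|
| 0.7 | 0.950/0.930 = 1.022 | 0.925/0.895 = 1.034 | 0.900/0.860 = 1.047 |
| 0.8 | 0.950/0.920 = 1.033 | 0.925/0.880 = 1.051 | 0.900/0.840 = 1.071 |

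That is 2% to 7%. It takes the trait to lower cost; if the trait raised cost, the sign would reverse.

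*Against sampling error.* The shares in 9.3.1 times the 1,798 in 9.5 give about 775, 214, 187, 237 and 387 patients (total 1,800; the shares sum to 100.1%, so this is rounding). In units of the cost SD, unweighted and with a common SD, SE = √(1/n1 + 1/n2), and the difference detectable with 80% power at two-sided 0.05 is (1.960 + 0.842) × SE.

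- Rapid decliners vs highly adherent: SE = √(1/775 + 1/387) = 0.062; detectable difference 0.174.
- Gradual decliners vs highly adherent: SE = √(1/775 + 1/187) = 0.082; detectable difference 0.228.

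Bias in SD units = (difference in trait prevalence) × (cost shift in SD). Prevalence differences of 0.10 to 0.40 and shifts of 0.1 to 0.5 SD give 0.01 to 0.20 SD. With no true effect, the chance of a nominally significant rapid-vs-high contrast is then 5.3% at 0.01 SD, 16% at 0.06, 30% at 0.09 and 90% at 0.20. For gradual-vs-high it runs from 5.2% to 69%.

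*Linking the two.* If the cost SD is 1 to 2.5 times the mean (assumed), 2% to 7% is about 0.02/2.5 = 0.01 SD to 0.07/1 = 0.07 SD, the lower part of that range. A 7% bias reaches 0.20 SD only if the SD is 0.07/0.20 = 35% of the mean.

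**The case against.** The case on the other side has substance.

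- **Control is partial, not absent.** A stable self-care trait that lowers follow-up cost should also show in baseline cost. Baseline spending by setting, ED use, medication count, pulmonology visits and the deprivation index are all in the roster. The eligibility rules in 9.2.2 (continuous coverage, no Medicaid dual eligibility, no skilled nursing, long-term care or hospice claims) narrow differences in function and access. This stands, and it makes 2% to 7% a figure before adjustment.
- **Direction is not fixed.** A reader might infer that highly adherent patients will look cheaper whatever nintedanib does. The documents do not support that. The primary outcome sums all medical services, so engaged patients could have fewer admissions but more outpatient and Part B spending. Section 7 cites a study of antihypertensives in which lower adherence went with more general-practitioner visits but not with hospitalizations.
- **The limitation is open-ended.** Section 9.9 offers disease severity as an example, not a closed list, and the objectives claim only association. This stands as a general caveat. However, 9.9 concerns determinants that claims do not contain. Regularity of filling other medicines can be derived from claims, so it can be adjusted for as well as acknowledged.
- **A falsification outcome would not settle it.** Injury hospitalization might seem a natural negative control. The exclusion of follow-up facility claims may remove many serious injuries. The 11-patient output rule in 9.6 needs event rates of about 11/187 = 5.9% (gradual) or 11/387 = 2.8% (rapid). Four contrasts at 0.05 would give up to 1 − 0.95⁴ ≈ 19% false alarms if independent. A difference could reflect frailty, and a null would not exclude confounding.

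**Conclusion.** The gap is real: the single roster behind both models has no direct measure of general adherence behaviour, and the planned double robustness does not close it. The contrasts may therefore carry residual healthy-adherer bias. Its size and direction cannot be set from the documents. On assumed inputs and before adjustment it runs from negligible (0.01 SD) to larger than the detectable difference for the largest contrast (0.20 SD against 0.174 SD); the 2% to 7% cost illustration sits towards the low end unless cost varies unusually little.

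A reader might go further and conclude that the design cannot control this bias at all, or that any cost difference found will be spurious. Neither follows, because the use and spending covariates give some control and nothing in the documents shows how much bias remains. This is a worthwhile, inexpensive improvement to the adjustment set and to the interpretation, not a defect that invalidates the analysis.

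**What to change.** Add two baseline covariates to 9.3.3, so that they enter both the multinomial logit and the outcome GLM:

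- (a) mean PDC over the 12 baseline months across a prespecified list of chronic non-antifibrotic medicine classes, with a separate category for patients taking none of them;
- (b) an indicator for any Part B-billed preventive service, such as influenza vaccination, in the baseline period.

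Report weighted balance on both across the five groups. In 9.9, name healthy-adherer bias as a reason the contrasts may not be attributable to nintedanib adherence.

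Injury hospitalization in follow-up may be reported as an exploratory falsification outcome if counts allow, but it should not dictate the conclusion.

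The cost is a little more programming on data already held and two more covariates in each model. Baseline PDC is itself an imperfect proxy for the trait, so the wording in 9.9 is needed even after the covariates are added.

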Population:	The study sample will consist of community-dwelling Medicare beneficiaries with IPF who initiate treatment with nintedanib.	
Variables:	
The main exposure will be a five-category measure of adherence trajectory to nintedanib in the year following initiation.
 
Outcomes will reflect inpatient hospitalization (any and number of days) and health care spending for both all-cause and IPF-related care.
 
A range of covariates will be measured during the baseline period and at the index date, including baseline patient demographic characteristics (e.g., age, sex, race/ethnicity), residential location, clinical characteristics (e.g., comorbidity index, IPF-related health care costs and use), and all-cause health care costs and use.
	
Data sources:	This study will use administrative enrollment and claims data from the U.S. federal Medicare program for beneficiaries aged 65 years and older who were continuously enrolled in Original Medicare insurance coverage, including Parts A, B and D. The study will use Medicare data covering the period from October 1, 2013, through December 31, 2020.	
Study size:	Based on our prior study, the sample for analysis of the primary outcomes will consist of 1,798 Medicare beneficiaries with IPF who initiated nintedanib between October 1, 2014, and December 31, 2018. The sample available for the secondary outcomes will be smaller by an unknown amount due to loss to follow-up.	
Data analysis:	
Mean health care cost and use outcomes will be compared between pairs of nintedanib adherence trajectory membership categories using a regression modeling framework. Unadjusted means will be compared first using an “empty” linear regression model specification (with no covariates or weights). Adjusted means will then be compared using a “doubly robust” generalized linear model (GLM) specification.
 
Potential confounding by observed covariates will be addressed in two ways to achieve double robustness. The first way will be to calculate observation-level inverse propensity weights that balance covariates
	

BOEHRINGER INGELHEIM Group of Companies**NIS Protocol****BI Study Number 1199-0520****Page 9 of 35****c42255024-02**

Proprietary confidential information © 2023 Boehringer Ingelheim International GmbH or one or more of its affiliated companies

Name of company: Boehringer Ingelheim			
Name of finished medicinal product: Nintedanib (Ofev)			
Name of active ingredient: Nintedanib (Ofev)			

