9.3.2 Outcomes

The primary outcome will be total all-cause medical costs, which will be calculated as the sum of total amounts paid (by payers and patients) for all medical services. Types of medical services covered by Medicare include inpatient facility, outpatient facility, skilled nursing facility, home health care, hospice, durable medical equipment, and clinician office visits (and other services covered under the Part B benefit). This outcome will exclude spending on outpatient pharmacy (as covered under the Part D benefit).

The secondary outcomes will be:

1. Total IPF-related medical costs, which will be calculated as the sum of total amounts paid (by payers and patients) for all medical services for an IPF-related reason (at least one IPF diagnosis code).
2. All-cause inpatient hospitalization
3. IPF-related inpatient hospitalization.

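### Double robustness is claimed for every use and spending model, but the planned non-Poisson log-link cost GLM and some two-part models do not have it

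*Combined protocol and SAP*

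**What the plan says.** The Abstract states the aim: "Potential confounding by observed covariates will be addressed in two ways to achieve double robustness". Section 9.7.1 repeats it for the main analysis. The weights (IPTW and MMWS) come from one multinomial logit model of trajectory group, and then "observed covariates will be added to the GLM specification". The conclusion drawn is "Combining weighting with regression adjustment yields a double robustness property that attenuates bias" if either the treatment model or the GLM for use or spending is misspecified.

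The same section lets the outcome model vary:

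- **Any hospitalization:** probably logistic.
- **Total length of stay (LOS):** possibly one-part Poisson "if the proportion of patients with zero days of hospitalization is sufficiently low (less than 10%), or a two-part model", for which logit plus Poisson is the example given.
- **Costs:** if the "outcome has a pile-up at zero, a two-part model will be estimated"; otherwise "a GLM with a log link and a distribution family decided by application of the modified Park test will be estimated". The family of the second part of a two-part cost model is not stated.

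Section 9.3.2 makes cost the primary endpoint: "The primary outcome will be total all-cause medical costs". Results are to be reported as average marginal effects on the outcome scale. Group-by-covariate interactions are not mentioned.

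**The concern.** Double robustness has two halves. If the outcome model is right, a wrong propensity model does no harm; that half holds for every family and is not in dispute. The other half says that correct weights rescue a wrong outcome model. For a weighted GLM that half depends on the family and link, and the plan states it without that condition.

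The primary outcome can fall in an unprotected branch. If costs show no pile-up at zero and the Park test selects gamma, for example, the weights do not assure protection against a wrong cost model. A reader of the report would be told that they do. The limitations in Section 9.9 do not mention this.

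**Working it through.** The plan gives no figure to reproduce here, so the check is algebra followed by large-sample limits.

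**1. One-part models.** With correct weights w = 1/P(group g | x), the weighted mean of (Y - mu_g) in group g tends to E[Y(g)] - E[mu_g(X)]. The averaged prediction is therefore right, even if mu is wrong, when the fit forces the sum of w(Y - mu) to zero in each group. Under a log link with variance function V, the score is the sum of w(Y - mu)·mu/V(mu)·x = 0:

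- Poisson, V = mu: sum of w(Y - mu) = 0. Protected.
- Gamma, V = mu²: sum of w(Y - mu)/mu = 0. Not protected in general.
- Inverse Gaussian, V = mu³: sum of w(Y - mu)/mu² = 0. Not protected.
- Gaussian, V = 1: sum of w(Y - mu)·mu = 0. Not protected.

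Logistic regression has the canonical link and is protected.

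**2. Two-part models.** Let D indicate Y > 0, p the fitted probability and m the fitted positive mean. Then Y - pm = D(Y - m) + (D - p)m. The first term has weighted mean zero if the second part is Poisson or is correct. The second is assured to be zero only if the logit is correct. So logit plus Poisson keeps the property when the logit is right, and otherwise it is not assured.

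**3. Size for costs.** The group shares are from Section 9.3.1 (43.1/11.9/10.4/13.2/21.5%). Everything else is assumed:

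- one N(0,1) covariate, with exposure log-odds slopes 0/0.2/0.3/0.4/0.5;
- cost $20,000 in the highly adherent group at covariate 0;
- group cost ratios 1/1.05/1.10/1.15/1.20 and log slope 0.4;
- fitted models with main effects only.

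The true rapid-minus-high differences are:

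- Additive mean ($6,000 per SD in every group): 20,000 × 0.20 = $4,000.
- Quadratic 0.1: 20,000 × 0.20 × 0.8^(-1/2) × exp(0.1) = $4,942.
- Interaction d in rapid decliners: 20,000 × [1.2·exp((0.4 + d)²/2) - exp(0.08)]. For d = -0.2 this is 20,000 × (1.2242 - 1.0833) = $2,819; for d = +0.2, $7,067; for d = -0.1, $3,439; for d = +0.1, $5,530.

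The weighted scores were solved by 80-point Gauss-Hermite quadrature. Coverage is from 1,500 simulated samples per scenario with n = 1,798, cost CV 1.5 and estimated weights.

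| Misspecification | Gamma + IPTW bias | In dollars | Poisson + IPTW bias | Gamma 95% CI coverage |
|---|---|---|---|---|
| Additive mean | +9% | about +370 | 0% | 94-95% |
| Quadratic 0.1 | -2% | -98 | 0% | 94-95% |
| Step 0.3 at +1 SD | -1% | | 0% | |
| Interaction -0.1 | +27% | about +940 | 0% | 95% |
| Interaction +0.1 | -20% | about -1,080 | 0% | 90% |
| Interaction -0.2 | +62% | +1,761 | 0% | 91% |
| Interaction +0.2 | -33% | -2,338 | 0% | 82% |

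Poisson and augmented gamma had 95-96% coverage. Gamma with group-specific slopes had at most 2% bias.

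**4. Does weighting at least attenuate?** Compared with the same gamma model unweighted, correct weights enlarged the bias in 9 of 14 cases (seven scenarios, two confounding directions). The additive case went from +5% to +9% and the -0.2 interaction from +29% to +62%. With confounding reversed, the weights helped: +11.5% to +9%, and +95% to +62%.

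**5. Size for LOS, logit plus Poisson.** With the zero share varied from 10% to 90%, bias was at most 1% for missed logit curvature, -4% to -10% for an omitted logit interaction of +0.2, and +4% to +17% for -0.2. It was 0% when the logit was right.

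**The case against.** The strongest reply concerns size. The primary outcome is affected only through a chain of conditions: an unprotected branch must be entered, the outcome model must be wrong and the propensity model right. The documents give no zero share, and the Park test could select Poisson. In the simulations it chose gamma in 98-100% of runs, but costs were generated with constant CV, so that result was built in.

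Several further points stand:

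- **Large bias needs an omitted interaction.** The additive case is itself an interaction on the log scale, because equal dollar slopes are combined with unequal group baselines. If the additive mean is scaled proportionally across groups, the bias is +0.6%.
- **Percentages flatter the effect when the true difference is small.** Against a sampling SD of about $2,374, the biases are 98/2,374 = 0.04 SD (quadratic), 370/2,374 = 0.16 SD (additive) and about 0.4 to 0.45 SD (interactions of ±0.1). For interactions of -0.2 and +0.2 they reach 1,761/2,374 = 0.74 and 2,338/2,374 = 0.98 SD.
- **The count of 9 in 14 is fragile.** Four of the nine are quadratic or step cases with at most 2% bias, and a step at 0 instead of +1 SD gives 8. The additive and interaction cases split evenly by confounding direction.
- **MMWS was not part of these calculations.** It stratifies, so it balances only approximately. One large simulated set with quintile strata gave Poisson plus MMWS contrasts off by 2% to 7%. Poisson plus IPTW in the same set was off by up to 6% where its limit is zero, so noise is substantial.
- **Unmeasured severity is untouched.** Section 9.9 concedes that the claims data are ones "which do not include important determinants of health care resource use and cost outcomes", with IPF severity as the example.

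These points limit the practical effect. They do not restore the property, and the plan's softer verb, attenuates, is not assured either.

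**Conclusion.** The concern holds. The double-robustness statement is too broad for planned branches of the primary analysis: a log-link cost GLM with a non-Poisson family, and a two-part model whose logit is wrong or whose non-Poisson second part is misspecified. The logistic model, one-part log-link Poisson, and logit plus Poisson with a correct logit all keep the property under IPTW.

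The algebra is firm; the bias sizes rest on assumed misspecification. Missed curvature or a step costs 1% to 2% and coverage is hardly affected where it was simulated. Omitted group-by-covariate interactions cost roughly 20% to 60% of the cost difference, with coverage as low as 82%. The point should be corrected before the results are described as doubly robust, but it does not invalidate the planned analysis.

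**What to change.** 1. For cost and total LOS, do one of the following:
   - Add to each group's averaged prediction, from the Park-selected or two-part model, that group's weighted mean residual: sum of w(Y - fitted)/sum of w over members of the group. Then take differences (augmented IPW).
   - Report, alongside the planned model, a one-part log-link quasi-Poisson fit with the same IPTW and robust standard errors, whatever the zero share.
2. State whether group-specific covariate slopes will be fitted. In these scenarios they removed most of the cost bias.
3. In the Abstract and Section 9.7.1, keep the doubly robust label for estimators that have the property, and describe the MMWS analyses as approximate in this respect.

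The cost is a few sentences and lines of code, plus some precision. When the gamma model is exactly right, the SD goes from $2,374 to $2,415 (1.7%) and from $2,324 to $2,405 (3.5%) in two sets of 1,500 runs. Under missed curvature it goes from $2,793 to $3,027 (8%). The gain depends on a correct propensity model and does nothing for unmeasured severity.
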